#### 11 MEASUREMENT OF EFFECT

#### 11.1 Antitumor Effect-Solid Tumors

For the purposes of this study, patients should be re-evaluated for response 8 weeks after the initial treatment, 16 weeks after treatment, and at 6 month intervals thereafter.

Response and progression will be evaluated in this study using the new international criteria proposed by the Response Evaluation Criteria in Solid Tumors (RECIST 1.1) Committee (30). Changes in only the largest diameter (unidimensional measurement) of the tumor lesions are used in the RECIST criteria.

The RECIST read at 16 weeks will be used to determine the objective response rate for the primary endpoint of this study.

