#### 11.3 Disease Parameters

Measurable Disease: Measurable lesions are defined as those that can be accurately measured in at least one dimension (longest diameter to be recorded) as  $\geq 0.5$  cm with diagnostic techniques (CT, PET/CT (all are optional), or MRI). All tumor measurements must be recorded in centimeters.

Non-Measurable Disease: All other lesions (or sites of disease), including small lesions (longest diameter <0.5 cm with diagnostic techniques), are considered non-measurable disease. Bone lesions, leptomeningeal disease, ascites, pleural/pericardial effusions, lymphangitis, inflammatory breast disease, and cystic lesions are all non-measurable.

Target Lesions: Target lesion in this study will be considered metastatic sites up to a maximum of 3 lesions per patient. They should be recorded and measured at baseline. Target lesions should be equal to or larger than 1.0 cm in the smallest

cross-sectional diameter on CT or MRI and/or any lesion that shows increase metabolic uptake on PET/CT scans.

Non-Target Lesions: Non-Target lesion in this study will be considered metastatic sites up to a maximum of 10 lesions per patient. They should be recorded and measured at baseline. Non-target lesions should be equal to or larger than 0.5 cm in the smallest cross-sectional diameter on CT or MRI and/or any lesion that shows increase metabolic uptake on PET/CT scans. Importantly, a sum of the longest diameter (LD) for all *non-target* lesions will be calculated and reported as the baseline sum LD. The baseline sum LD of the *non-target* lesions will be used as reference by which to characterize the objective tumor response.

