#### 11.5 Response Criteria (via RECIST 1.1)

#### 11.5.1 Evaluation of Target Lesions

Complete Response (CR): Disappearance of all targeted and *Non-Targeted* lesions

Objective Response (OR): At least a 30% decrease in the sum of the

longest

diameter (LD) of targeted and *Non-targeted* lesions,

taking as reference the baseline sum LD

Progressive Disease (PD): At least a 20% increase in the sum of the LD of

Targeted or Non- Targeted lesions, taking as reference the smallest sum LD recorded since the treatment started or the appearance of one or more new lesions

Stable Disease (SD): Neither sufficient shrinkage to qualify for PR nor

sufficient

increase to qualify for PD, taking as reference the

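### Section 11 scores every lesion by longest diameter, with no lymph-node rule, so cleared nodal disease can be read as stable disease in the primary endpoint

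*Combined protocol and SAP*

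**What the plan says.** Section 11.1 names the standard: "Response and progression will be evaluated in this study using the new international criteria proposed by the Response Evaluation Criteria in Solid Tumors (RECIST 1.1"). Its next sentence gives the protocol's account of that standard: "Changes in only the largest diameter (unidimensional measurement) of the tumor lesions are used in the RECIST criteria". The 16-week read decides the primary endpoint.

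Section 11.3 sets the sizes:
- Measurable disease: "Measurable lesions are defined as those that can be accurately measured in at least one dimension (longest diameter to be recorded) as" at least 0.5 cm.
- Target lesions: "Target lesions should be equal to or larger than 1.0 cm in the smallest" cross-sectional diameter.
- Non-target lesions: "Non-target lesions should be equal to or larger than 0.5 cm in the smallest cross-sectional diameter on CT or MRI".
- For both target and non-target lesions, increased PET uptake is an alternative route of entry.
- Non-target lesions "will be considered metastatic sites up to a maximum of 10 lesions per patient", and the baseline reference for response is "a sum of the longest diameter (LD) for all" non-target lesions.

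The smallest diameter is only an entry size. It never enters the sum. Section 11.3 lists disease that is always non-measurable (bone lesions, effusions, cystic lesions and others), and nodes are not on the list.

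Section 11.5.1 defines complete response (CR) as "Disappearance of all targeted and" non-targeted lesions. The 30% and 20% thresholds apply to the sum of longest diameters (LD), and anything between them is stable disease (SD). Section 15.5 makes the primary endpoint a fall of at least 30% in the sum LD of the non-targeted lesions.

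Neither section 11 nor section 15 mentions lymph nodes. They occur only in the background biology of sections 4.1 and 4.4.

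**The concern.** A lymph node is a normal organ. When the tumour in it clears, the node shrinks towards normal size but stays visible on the scan. This is general anatomy and is not stated in the documents. A rule based on longest diameter and disappearance therefore leaves a non-tumour remainder in the sum, with two effects.

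- Cleared nodal disease cannot be CR. It also fails the primary endpoint if the remainder keeps the fall in the sum below 30%.
- A small node that has been called metastatic and does not shrink adds a constant to baseline and follow-up, so the other lesions must shrink by more than 30%.

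In either case a true responder is counted as a non-responder. If this happens in both arms, both response rates fall and the difference between them narrows. A patient misread as SD could also enter the secondary endpoint of stable disease for at least 6 months (section 15.1.2).

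**Working it through.** The plan gives no figure on this point, so there is none to reproduce. The thresholds below are the protocol's. All lesion sizes are assumed, because the documents give no nodal sizes.

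**1. A lone node that clears.** Fall = (baseline - follow-up) / baseline. Each example starts at 15 mm short axis and ends at 9 mm.

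| Node, longest x short (mm) | Fall, longest | Fall, short axis | Read under the plan |
|---|---|---|---|
| 20x15 to 15x9 | 5/20 = 25.0% | 6/15 = 40.0% | SD |
| 18x15 to 13x9 | 5/18 = 27.8% | 40.0% | SD |
| 25x15 to 18x9 | 7/25 = 28.0% | 40.0% | SD |
| 20x15 to 13x9 | 7/20 = 35.0% | 40.0% | response |

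The last row matters: a node that remains visible still counts as a response if its longest diameter falls by 30% or more. In general, a cleared node with residual longest diameter r reaches -30% only if its baseline is at least r/0.7. Assumed residuals of 10, 12 and 14 mm need baselines of 14.3, 17.1 and 20.0 mm.

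**2. Unchanged small nodes in the sum.** Take one 30 mm metastasis and k nodes of 11 mm longest diameter that do not change. The fall needed in the metastasis is 0.3 x (30 + 11k) / 30:
- k = 0: 30%
- k = 1: 0.3 x 41/30 = 41%
- k = 2: 0.3 x 52/30 = 52%
- k = 3: 0.3 x 63/30 = 63%

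With 8 mm nodes instead, a lesion going from 20 to 12 mm (-40%) becomes 8/28 = -28.6% with one such node, which is SD. A lesion going from 30 to 18 mm becomes 12/46 = -26.1% with two.

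**3. What lost responders would cost.** Suppose a fraction m of responders in each arm is read as SD. The rates become p(1 - m) and the difference shrinks by the same factor. For 61% vs 81% and m = 10%, they become 54.9% vs 72.9%, a difference of 18 points instead of 20. Power is for two proportions with 73 per arm and one-sided 5% (section 15.2 prints 0.05%, read here as 5%), normal approximation without continuity correction:

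| Rates (section 15.2) | m = 0 | 5% | 10% | 20% |
|---|---|---|---|---|
| 61% vs 81% | 85.2% | 79.4% | 73.6% | 62.2% |
| 40% vs 53% | 47.2% | 44.3% | 41.5% | 36.4% |
| 25% vs 33% | 28.0% | 26.8% | 25.6% | 23.2% |

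The values of m are assumed. The table shows how sensitive power is to such a loss. It does not estimate the loss in this trial.

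**The case against.** The strongest reply is that RECIST 1.1 governs. It is named in 5.1.2, 6.2, 6.3 and 11.1 and in the heading of 11.5, and the study radiologist reviews all responses (11.5.5). The sentence on the largest diameter describes what the criteria use and does not announce a departure from them, so a reader trained in those criteria may apply their node rules anyway. This stands in part: the documents do not establish that nodes will in fact be scored by longest diameter. But every operative sentence in 11.1, 11.3, 11.5.1 and 15.5 uses longest diameter, and 11.3 sets its own lesion counts and sizes. A reader who follows the written text will score nodes that way, and two readers could differ on the same node.

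Three stronger readings are tempting and are not supported:
- *Blocking CR lowers the primary response rate.* It does not by itself. The endpoint is CR plus PR, and a patient who misses CR still counts if the sum falls by 30%.
- *The protocol directs normal nodes into the sum.* It does not. Section 11.3 admits only metastatic sites, so a small node enters only if it is called one. The 0.5 cm limit and the PET route give little protection against that call. That such nodes then stay unchanged is an assumption.
- *The comparison is biased towards one arm.* The same rule applies to both arms, and nothing in the documents suggests that nodal disease is unevenly distributed.

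**Conclusion.** The point holds as a weakness in the written response rules. Section 11 cites RECIST 1.1 but spells out scoring by longest diameter only, with no node exception. Followed as written, that scoring can turn a patient whose nodal disease has cleared into a non-responder for the primary endpoint. This occurs only when the sum LD falls by less than 30%.

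For a single patient the effect can decide the outcome: -25% against -40% for one node, or 41% instead of 30% shrinkage required elsewhere, both with assumed sizes. For the trial its size is unknown, because the documents give neither the share of patients with nodal disease nor the nodal sizes expected. The expected consequence is diluted response rates and some loss of power in both arms, not directional bias. The correction is worth making because it is cheap and because it concerns the measurement behind the primary endpoint.

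**What to change.** Amend four places together:
- **11.1:** replace the sentence limiting measurement to the largest diameter. Use short axis for lymph nodes and longest diameter for all other lesions.
- **11.3:** enter a node in the sum by its short axis, and set a node-specific minimum short axis for entry.
- **11.5.1:** state the short axis below which a node counts as resolved for CR.
- **15.5:** define the 30% fall on this same sum, which is then no longer purely a sum of longest diameters.

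Take both node limits from the RECIST 1.1 criteria that the protocol already names. The documents do not give them. Working values of 15 mm for entry and under 10 mm for normal are assumptions to be checked against those criteria. With those values, a node that enters the sum and returns to normal falls by more than (15 - 10)/15 = 33.3%, so cleared disease confined to such nodes would always pass the 30% threshold.

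The cost is protocol and CRF wording. The scans are the same, and any read already made would need nodes re-measured on the stored images. The downside is that some small nodes no longer contribute to the sum. Section 11.3 must therefore be aligned with 5.1.2, which already sets measurable disease by RECIST 1.1, so that no enrolled patient is left without a lesion to score.

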#### 11.2 Definitions

Evaluable Population: will consist of all patients who have received at least 1 cycle of CBI with or without SBRT.

Safety Population: Will consist of all subjects who were enrolled and have received at least 1 cycle of CBI with or without SBRT. This will be used to assess the clinical safety and tolerability of the study.

Evaluable for Objective Response: Patients who have measurable disease present at baseline and have received at least 1 cycle of CBI, and have had their disease re- evaluated will be considered evaluable for response. These patients will have their response classified according to the definitions stated below.

#### 11.3 Disease Parameters

Measurable Disease: Measurable lesions are defined as those that can be accurately measured in at least one dimension (longest diameter to be recorded) as  $\geq 0.5$  cm with diagnostic techniques (CT, PET/CT (all are optional), or MRI). All tumor measurements must be recorded in centimeters.

Non-Measurable Disease: All other lesions (or sites of disease), including small lesions (longest diameter <0.5 cm with diagnostic techniques), are considered non-measurable disease. Bone lesions, leptomeningeal disease, ascites, pleural/pericardial effusions, lymphangitis, inflammatory breast disease, and cystic lesions are all non-measurable.

Target Lesions: Target lesion in this study will be considered metastatic sites up to a maximum of 3 lesions per patient. They should be recorded and measured at baseline. Target lesions should be equal to or larger than 1.0 cm in the smallest

cross-sectional diameter on CT or MRI and/or any lesion that shows increase metabolic uptake on PET/CT scans.

Non-Target Lesions: Non-Target lesion in this study will be considered metastatic sites up to a maximum of 10 lesions per patient. They should be recorded and measured at baseline. Non-target lesions should be equal to or larger than 0.5 cm in the smallest cross-sectional diameter on CT or MRI and/or any lesion that shows increase metabolic uptake on PET/CT scans. Importantly, a sum of the longest diameter (LD) for all *non-target* lesions will be calculated and reported as the baseline sum LD. The baseline sum LD of the *non-target* lesions will be used as reference by which to characterize the objective tumor response.

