#### 11.5.4 Clinical Response Parameters

**Time to Local Progression (TTLP)** is defined as the elapsed time from the start of treatment to the date of documented local progression or death, whichever happens earliest.

**Progression-Free Survival (PFS)** is defined is the time from starting treatment to the time of first documented tumor progression or death due to any cause, whichever occurs first. Death is considered as an event here. For subjects whose disease does not progress or who do not die, PFS will be censored at the time of the last visit.

*Time to Progression (TTP)* is defined as the time from starting treatment to the time of first documented tumor progression. Subjects who do not progress will be censored at the time of the last contact. In addition, death from any cause will also be censored.

Overall Survival (OS) is defined as the time from starting treatment until death due to any cause. For subjects who do not die, time to death will be censored at the time of last contact.

**Locoregional Control (LRC)** is defined as the time from starting treatment until local and/or regional relapse is documented

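### The printed progression rule gives no written route to PD for worsening of baseline non-measurable disease, so some progressions are recorded late or censored, and CR can be called while that disease persists

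*Combined protocol and SAP*

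**What the plan says.** Section 11.3 separates measurable from non-measurable disease: "Bone lesions, leptomeningeal disease, ascites, pleural/pericardial effusions, lymphangitis, inflammatory breast disease, and cystic lesions are all non-measurable". Target and Non-Target lesions are then defined by size or by PET uptake. For the latter, "Non-target lesions should be equal to or larger than 0.5 cm in the smallest cross-sectional diameter on CT or MRI and/or any lesion" with raised PET uptake qualifies. Non-Target lesions are handled by measurement: "a sum of the longest diameter (LD) for all *non-target* lesions will be calculated and reported as the baseline sum LD".

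Section 11.5.1 gives two triggers for PD. The first is "At least a 20% increase in the sum of the LD of" Targeted or Non-Targeted lesions; the second is a new lesion: "taking as reference the smallest sum LD recorded since the treatment started or the appearance of one or more new lesions". CR is disappearance of the Targeted and Non-Targeted lesions. Section 11.5 contains no qualitative evaluation of any other disease.

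Section 11.1 names the governing criteria: "Response and progression will be evaluated in this study using the new international criteria proposed by the Response Evaluation Criteria in Solid Tumors" (RECIST 1.1). It goes on to describe those criteria as using change in largest diameter alone. Section 11.2 says evaluable patients are classified by the definitions that follow it, which are the printed ones.

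Section 11.5.4 says PFS "is defined is the time from starting treatment to the time of first documented tumor progression or death due to any cause", with censoring at the last visit if neither occurs. Section 15.5 defines the primary response as a 30% fall in the Non-Targeted sum, with no condition on other disease.

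**The concern.** The listed forms of disease can be present at entry. Section 5.1 asks for one measurable site that will not be irradiated and a histologically confirmed malignancy, and Section 5.2 excludes none of the listed forms. Some patients will carry effusions, ascites or bone disease alongside measurable nodules, and in some of them that disease will be the first to worsen.

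Read literally, the plan has no rule that turns such worsening into PD. The event is then recorded only when something else qualifies (a rise in a sum, a new lesion, or death). If visits stop first, it is censored. That censoring would be informative, because the patient leaves observation on account of worsening. Section 6.7 mentions clinical as well as radiographic progression as the point up to which other therapy is forgone, but Section 11.5.4 does not list clinical progression as a PFS event.

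At stake are PFS, duration of response and stable disease of at least 6 months. To a lesser degree, so is the 16-week response count.

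**Working it through.** The documents state no figure for this point, so the main check is textual.

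**1. Cases put through the printed rules.** Each patient has baseline non-measurable disease that is not captured as a PET-avid lesion.

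| Course | Sections 11.5.1 and 15.5 give |
|---|---|
| Sums unchanged, ascites clearly worse, no new lesion | Rise 0%, below 20%: stable disease |
| Sums down by 30%, effusion clearly worse, no new lesion | Responder at 16 weeks |
| All listed lesions gone, ascites still present | CR |

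The first row affects PFS, duration of response and 6-month stable disease. The second reaches the primary endpoint: with 73 patients per arm, each such patient moves that arm's rate by 1/73 = 1.4 percentage points. The third does not change the primary count, since a patient called CR instead of PR is a responder either way.

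**2. Illustration of the delay in PFS.** All inputs are assumptions:
- true PFS is exponential with median m = 6.0 months, so λ = ln 2 / 6 = 0.1155 per month;
- a share f of first progressions lies only in non-measurable disease (5%, 10%, 20%);
- these are recorded after an extra exponential delay with mean d (2 or 4 months), so μ = 1/d;
- there is no censoring.

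The recorded survival function is

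S(t) = (1 − f)·e^(−λt) + f·[μ·e^(−λt) − λ·e^(−μt)] / (μ − λ),

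and the recorded median solves S(t) = 0.5.

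| f | d = 2 months | d = 4 months |
|---|---|---|
| 5% | 6.12 | 6.21 |
| 10% | 6.23 | 6.42 |
| 20% | 6.46 | 6.85 |

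Check of the last cell at t = 6.85: e^(−λt) = 0.453 and e^(−μt) = 0.180. The bracket divided by (μ − λ) is (0.25 × 0.453 − 0.1155 × 0.180)/0.1345 = 0.688, so S = 0.8 × 0.453 + 0.2 × 0.688 = 0.50. The shift is about 2% to 14%. With m = 4.0 months the same formula gives 4.11 to 4.75 months, about 3% to 19%. A simulation of 400,000 patients per cell agrees to within 0.02 months.

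**3. The opposite pull in the same rule.** Section 11.5.1 sets no minimum absolute increase, and Section 11.3 admits Non-Target lesions from 0.5 cm. A single lesion going from 0.5 to 0.6 cm has grown by 0.1/0.5 = 20%. One millimetre is then PD, which shortens recorded PFS in other patients.

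**The case against.** The strongest reply is that the plan cites RECIST 1.1 in Section 11.1 and in the heading of Section 11.5, so a reader could apply the cited criteria in full. The documents do not reproduce those criteria. Section 11.1 describes them as largest-diameter change only, and Section 11.2 points to the printed definitions. A radiologist would have to look past Section 11.1 to find a rule for this disease. The citation therefore leaves an ambiguity and does not close the gap.

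Four further points stand and limit the conclusion.

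- A reader might infer that such worsening is never progression. The text does not support that. Section 11.3 admits PET-avid lesions, so an avid bone lesion can enter the sums, although PET is optional and an effusion, ascites or leptomeningeal disease has no sensible diameter. Section 11.5.4 does not cite Section 11.5.1, and Section 11.4 does not bar clinical assessment.
- A reader might infer that PFS is overstated. New lesions, later growth and death still count, and the 20% rule without a minimum works the other way. The net sign cannot be fixed from the documents.
- Treating missed events as a plain cut in the hazard gives a median of 6/(1 − g), or 6.7 to 7.5 months for g = 10% to 20%. That is an upper bound. It lets a patient with overt worsening carry on at the ordinary remaining hazard, for a further 8.66/0.9 = 9.6 to 8.66/0.8 = 10.8 months on average before a counted event (8.66 = 6/ln 2). That is hard to credit.
- Both arms use the same rule, so a biased comparison between arms is not shown. PFS and 6-month stable disease are secondary, and Section 15.6 names no test for PFS.

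**Conclusion.** The gap is real and rests on the printed text. Baseline ascites, effusions, leptomeningeal disease, lymphangitis, and bone lesions not captured as PET-avid have no written route to PD, and CR can be called while they persist. Following the plan as written misclassifies patients who worsen only there: their progression is recorded late or lost to censoring. The same gap lets a patient with shrinking nodules and a worsening effusion count as a responder at 16 weeks.

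The size is unknown. The range of 6.12 to 6.85 months for a true 6.0-month median depends entirely on the assumed 5-20% share and the 2-4 month mean delay. It isolates this one gap and is not an estimate of net bias in PFS. The point should be corrected because it makes the progression-based endpoints hard to interpret. It does not show that the randomised comparison is biased.

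**What to change.** Reconcile Sections 11.1, 11.3 and 11.5.1 for endpoint classification:

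- add to PD: *or unequivocal worsening of non-measurable disease recorded at baseline*;
- require resolution of that disease for CR;
- state whether a patient who meets the 30% fall but has such worsening is a responder at 16 weeks;
- record the presence of non-measurable disease at baseline and its status (absent, present, worse) at each scan.

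The cost is a few sentences in Section 11 and one CRF field. The drawback is a qualitative judgement in a read that Section 11.5.5 assigns to the co-investigator radiologist without stating that it is blinded. Section 12.4 lists peritumoral infiltrate on chest imaging as a sign of radiation pneumonitis, so a loose judgement could differ by arm. 'Unequivocal' should therefore be defined before any reads are made, and treatment-related change in the irradiated field should not count as worsening. The missing absolute minimum in the 20% rule is a separate matter, but settling it in the same revision would remove the opposing source of error.
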